Although there will be readiness to address the AESI currently identified potential unexpected safety concerns related may arise during product development or after licensure; we aim that principles and designs in this protocol can also be applied to novel issues, which is why we created a decision framework to quickly assess which design may be most appropriate.

Each of the AESI listed in **Table 2** differs in terms of latency, acuity of onset, availability of empirical estimates for appropriate risk periods, and the effect of the event on subsequent likelihood of vaccination.

Criteria for determining the appropriate design for the event under study are described in **Annex 3**. Specific design recommendations for each AESI are provided in **Table 2** below.

Table 2. Assessment of the Suitability of Cohort, Case-Control, SCCS, SCRI and CCO designs for signal evaluation, by pre-identified AESI

Event	Cohort	Case-control	SCCS	SCRI	CCO
Enhanced disease following immunisation	X	✓	X	X	X
Multisystem inflammatory syndrome in children	✓	✓	✓ ^a	✓ ^a	✓
Acute respiratory distress syndrome	✓	✓	✓	✓	✓
Acute cardiovascular injury, including microangiopathy, heart failure, stress cardiomyopathy, coronary artery disease, arrhythmia, myocarditis	✓	✓	✓	✓	✓
Coagulation disorder, including deep vein thrombosis, pulmonary embolus, cerebrovascular stroke, limb ischaemia, haemorrhagic disease	✓	✓	✓	✓	✓
Generalised convulsion	✓	✓	✓	✓	✓
Guillain Barré Syndrome	✓	✓	✓	✓	✓
Diabetes (type 1 and unspecified type)	✓	✓	✓	X	X
Acute kidney injury	✓	✓	✓	✓	✓
Acute liver injury	✓	✓	✓	✓	✓
Anosmia, ageusia	✓	✓	✓	✓ ^a	✓
Chilblain-like lesions	✓	✓	✓	✓	✓
Single organ cutaneous vasculitis	✓	✓	✓	✓ ^a	✓

Event	Cohort	Case-control	SCCS	SCRI	CCO
Erythema multiforme	✓	✓	✓	✓ ^a	✓
Anaphylaxis	✓	✓	✓	✓	✓
Death (any causes)	✓	✓	✓	✗	✓
Sudden death	✓	✓	✓	✗	✓
Acute aseptic arthritis	✓	✓	✓	✓	✓
Meningoencephalitis	✓	✓	✓	✓	✓
Acute disseminated encephalomyelitis	✓	✓	✓	✓ ^a	✓
Narcolepsy	✓	✓	✓	✗	✗
Thrombocytopenia	✓	✓	✓	✓	✓
Transverse myelitis	✓	✓	✓	✓ ^a	✓
Preterm birth	✓	✓	✗	✗	✗
Major congenital anomalies	✓	✓	✗	✗	✗
Microcephaly	✓	✓	✗	✗	✗
Fetal growth restriction	✓	✓	✗	✗	✗
Gestational diabetes	✓	✓	✗	✗	✗
Preeclampsia	✓	✓	✗	✗	✗
Spontaneous abortions	✓	✓	✗	✗	✗
Stillbirth	✓	✓	✗	✗	✗
Induced abortions	✓	✓	✗	✗	✗
Termination of pregnancy for fetal anomaly (TOPFA)	✓	✓	✗	✗	✗
Neonatal death	✓	✓	✗	✗	✗
Maternal death	✓	✓	✗	✗	✗

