^a Suitability of the self-controlled designs is dependent upon availability of a purported risk period, which for some AESI is as yet unknown.

8 Research Question and Objectives

Note to future investigators using this template to develop a full study protocol: the wording of some sections of this protocol can be retained as-is or modified as appropriate in a final study protocol. Notes directly to the investigators in these sections are indicated in square brackets. As there are multiple potential COVID-19 vaccine products under development and additional adverse events may be identified, this protocol template refers generically to a <<COVID-19 vaccine product>> and at times, <<event>> which may be replaced with the name of the specific vaccines or adverse events being investigated. The language in some sections, however, describes general principles, issues, and considerations for the investigator and will require the investigator to develop those sections with study-specific content, as appropriate for the specific study being considered.

[For all designs, the secondary analysis of vaccine groups defined by vaccine platforms or components should be done if the products are hypothesized to have a similar safety profile across the grouped products. Also, if a safety concern for an adverse event has arisen around a specific vaccine product, then the analysis of all COVID-19 vaccine products combined should not be conducted for that event]

Primary objective: To determine whether there is an increased risk of pre-specified <<event>> following vaccination with specific <<COVID-19 vaccine product>> using study designs <<cohort, case-control, self-controlled, or case-crossover>> which allow for control of confounding.

Secondary objectives:

§ To determine whether there is an increased risk of pre-specified <<event>> in specific vaccine groups defined by platform and/or components (e.g. adjuvant)

§ To determine whether risk of <<event>> following vaccination with specific <<COVID-19 vaccine product>> differs by characteristics such as age, sex, comorbidities, infections, concomitant vaccinations, concomitant medications, and/or other characteristics.

9 Research Methods

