9.1.4 Case-crossover (CCO)

Retrospective (multi)-database case-only study that includes subjects who experienced << event >>, independent of vaccination. The CCO design considers the occurrence of << event >> as fixed event and the << COVID-19 vaccine >> exposure random. The design compares the odds of exposure in a specific time window retrospectively in time, where the odds of exposure is compared over these time periods. Index date for the case is the date of the event, index date for the control periods of the same person are distinct points in time prior to case occurrence. Index moment for the control window, should be distanced with at least the duration of the exposure window (**Figure 5**). It is likely that vaccinations will only be administered on weekdays therefore the index date for the control window should be matched on day of the week to have equal probability of exposure. Control periods should not extend in the period prior to launch of the vaccination since the probability of exposure would be zero. Due to unavoidable time trend in vaccination a case time control adaptation is required (Schneeweiss, 1997). The case-time-control design is an elaboration of the case-crossover design, which uses exposure history data from a traditional control group to estimate and adjust for the bias from temporal changes in prescribing.

Figure 5. Case-crossover design

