Annex 2. ENCePP Checklist for Study Protocols

The ENCePP Checklist for Study Protocols can be accessed and downloaded using the following link:
[http://www.encepp.eu/standards and guidances/checkListProtocols.shtml](http://www.encepp.eu/standards_and_guidances/checkListProtocols.shtml)

Annex 3. Criteria to determine whether Cohort, Case-Control, Self-Controlled Case Series, Self-Controlled Risk Interval or Case-crossover Can Be Used for Signal Evaluation

Based on the assumptions and requirements of each design, we provide a decision framework for determining when Cohort, Case-Control, Self-Controlled Case Series (SCCS), Self-Controlled Risk Interval (SCRI), and Case-Crossover (CCO) designs can be used for signal evaluation.

The decision framework described below is based on event criteria. However, the identification of a suitable comparator group (active or unvaccinated) and the ability to identify major confounders should also be considered to determine the appropriate study design (see [section 9.1](#)). Cohort and case-control designs are suitable to assess a majority of events. In general, when the data is already available in electronic health care databases, cohort analysis should be conducted since it will provide absolute and relative risk measures. Case control design may be efficient if additional data needs to be collected or exposure patterns are difficult to track over follow-up time, also they allow for matching on calendar time, which is relevant with strong temporal trends. Because cohort and case control designs use other subjects as comparator, residual confounding due to factors that are not easily measurable in EHR data (such as genetics, habits, socio-economic status, ethnicity) can remain. If this is suspected self-controlled designs may be more suitable, but they require accurate estimation of the risk window and onset of the event.

Decision Framework for Determining Suitability of cohort, case-control, SCCS, SCRI, CCO for signal evaluation

Event criteria	Cohort	Case-control	SCCS	SCRI	CCO
Event latency					
Long latency	✓	✓	○ ^a	✗	✗
Short latency	✓	✓	✓	✓	✓
Outcome onset					
Acute onset	✓	✓	✓	✓	✓
Gradual onset	✓	✓	○ ^a	✗	✗
Ability to define risk period for outcome following exposure					
Can be clearly defined	✓	✓	✓	✓	✓
Cannot be clearly defined	✓	✓	○	✗	✗
Effect of event on likelihood of vaccination					
Event does not affect likelihood of vaccination	✓	✓	✓	✓	✓

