Event temporarily decreases or increases likelihood of vaccination	✓	✓	✓	✓	✓
Event is a (permanent) contraindication to vaccination	O ^b	O ^b	O ^b	O ^b	✓
Event censors the period of observation for exposure (e.g., death or an outcome that increases the probability of death such as myocardial infarction)	✓	✓	X	X	✓
Event is independently recurrent	✓	✓	✓	✓	✓
Event is non-recurrent but rare	✓	✓	✓	✓	✓
Event is recurrent, and recurrent events are not independent (e.g., stroke)	✓	✓	O ^c	X	O
Temporal trends in vaccination					
Temporal trends in vaccination are not present during the study period	✓	✓	✓	✓	✓
Temporal trends in vaccination are present during the study period	✓	✓	✓	✓	O

Checkmark indicates design is suitable; X indicates not suitable; O indicates that the study design is possible under certain circumstances.

^a Suitable if prodromal symptoms before diagnosis of the outcome do not cause or prevent vaccination, either temporarily or permanently. To address this potential source of bias, every effort should be made to identify the onset of symptoms from the available data such as medical records, rather than relying on the date of diagnosis.

^b Suitable if the vaccine is given in a single dose. If the vaccine is given in multiple doses, the design is not suitable unless special analytic techniques are applied to handle censored, perturbed, or curtailed post-event exposures.

^c Suitable if appropriate adaptations to the self-controlled case series are applied (Farrington, 2010)

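### Case-crossover is ticked without condition for all-cause death, although a fall in vaccination before death would bias its odds ratio downward and case-time-control would not remove that bias

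*Protocol*

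**What the plan says.** Section 7, Table 2, gives design recommendations by adverse event. The row "Death (any causes" has a tick under CCO and no footnote. The table's only footnote, "Suitability of the self-controlled designs is dependent upon availability of a purported risk period", concerns unknown risk periods and is not attached to this row. Sudden death is a separate row, also ticked.

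Annex 3 holds the criteria behind the table. Three entries matter here:

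- The row "Event censors the period of observation for exposure (e.g., death or an outcome that increases the probability of death such as myocardial infarction" ticks CCO, again without a footnote.
- The row "Gradual onset" marks CCO as not suitable and SCCS as possible under footnote a.
- Footnote a reads "Suitable if prodromal symptoms before diagnosis of the outcome do not cause or prevent vaccination, either temporarily or permanently". It is attached to SCCS entries only.

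Section 9.1.4 treats the event "as fixed event and the << COVID-19 vaccine >> exposure random". On the placing of the windows it says: "Index date for the case is the date of the event, index date for the control periods of the same person are distinct points in". The rest of that sentence puts the control points before the event. The section also requires a correction: "Due to unavoidable time trend in vaccination a case time control adaptation is required". The correction is estimated from the exposure history of a conventional control group.

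**The concern.** A CCO compares exposure just before the event with exposure earlier in the same person. Absent a vaccine effect, vaccination must be equally likely in both windows. Section 9.1.4 accepts this principle: it matches control windows on weekday and bars windows before vaccine launch. It does not apply the principle to a person's health before the event. The Annex 3 row on censoring asks only whether exposure after the event is needed, which is a different question.

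All-cause death will include deaths that follow a period of decline. If vaccination is deferred in that period, the case window is under-exposed relative to the control window. Self-matching does not help, because the change occurs within the person. Case-time-control does not help either, because people who are not dying share the calendar trend but not the decline. The bias runs towards no harm, or apparent protection, for the gravest event on the list. A future protocol that takes over the tick takes over no warning.

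**Working it through.** The protocol states no odds ratio, sample size or withholding rate on this point, so there is no figure of its own to reproduce. The inputs below are assumptions, shown as ranges.

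**Formula.** Take one vaccination per person, a low vaccination rate, and case and control windows of equal length. Let T be the calendar trend in vaccination, and wH and wC the average share of vaccination withheld in the case and control windows among people who die.

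- Crude CCO odds ratio = RR × T × (1 − wH)/(1 − wC)
- Controls who are not dying estimate T only, so case-time-control odds ratio = RR × (1 − wH)/(1 − wC)

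**Assumed inputs.** Adjacent 28-day windows, which meet the minimum spacing in section 9.1.4. Length of decline uniform on 14 to 60 days. A share p of deaths is affected, and during decline the vaccination rate falls to a fraction q of normal.

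**Average share of each window covered by decline.**

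- Case window: [(28² − 14²)/2 + 28 × (60 − 28)] / 46 / 28 = (294 + 896)/46/28 = 0.924
- Control window: [28²/2 + 28 × (60 − 56)] / 46 / 28 = (392 + 112)/46/28 = 0.391

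Then wH = p(1 − q) × 0.924 and wC = p(1 − q) × 0.391.

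| p | q | p(1 − q) | 1 − wH | 1 − wC | Odds ratio, RR = 1 | Odds ratio, RR = 2 |
|---|---|---|---|---|---|---|
| 0.3 | 0.5 | 0.15 | 0.861 | 0.941 | 0.92 | 1.83 |
| 0.5 | 0.5 | 0.25 | 0.769 | 0.902 | 0.85 | 1.70 |
| 0.5 | 0.2 | 0.40 | 0.630 | 0.843 | 0.75 | 1.49 |
| 0.7 | 0.2 | 0.56 | 0.483 | 0.781 | 0.62 | 1.24 |

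**When a risk is fully masked.** The odds ratio reaches 1 when net withholding, 1 − (1 − wH)/(1 − wC), equals 1 − 1/RR: 17% for RR 1.2, 33% for 1.5, 50% for 2 and 67% for 3. In the table, the largest true RR that would read as 1 is 1/0.915 = 1.09 in the first row and 1/0.618 = 1.62 in the last.

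**Dependence on the length of decline.** With decline of 30 to 90 days, the null odds ratios run from 0.97 (first row) to 0.80 (last row). With 60 to 180 days, decline always covers both windows (56 days in all), so wH = wC and the odds ratio is 1.00.

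**Simulation check.** 300,000 cases and 300,000 controls without decline, adjacent 42-day windows, rising vaccination rate, RR = 2:

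- No withholding: crude 2.25, control trend 1.12, corrected 2.01. The correction does remove the calendar trend.
- 80% of deaths affected, 80% withheld over the last 42 days: corrected 0.75.
- Same, over the last 14 days only: corrected 1.56.
- Same, over 84 or 180 days: corrected 2.07 and 2.11. The downward bias is gone.

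**The alternative designs in the same model.** An unadjusted case-control comparison of exposure in the last 28 days has the null odds ratio 1 − wH: 0.86, 0.77, 0.63 and 0.48 for the four rows. It is never closer to 1 than the case-time-control value, because 1 − wC is at most 1. The cohort was not run separately, but it too compares dying with living people.

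**The case against.** The strongest reply is that the tick is not the protocol's last word. The document is a template, and section 9.1 requires a feasibility assessment and leaves the choice of design to the investigator. Section 7 refers the reader to Annex 3, where CCO is crossed out for gradual onset and for risk periods that cannot be clearly defined, and is conditional under temporal trends. Section 9.1.4 requires case-time-control, section 9.8 warns about trends in exposure, and section 9.2.3.4.2 asks for attention to healthy vaccinee bias and confounding by indication. That stands as far as it goes: CCO is not unconditional across the whole protocol. But the trend provisions deal with calendar time, the healthy vaccinee warning is tied neither to CCO nor to death, and the two cells an investigator would consult carry no condition.

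A reader might infer several stronger points that the documents do not support.

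- That the case window is under-exposed by construction. It is not. The bias needs withholding that differs between the windows, and the protocol nowhere says that vaccination is withheld near death.
- That the odds ratio hides the risk. In all four scenarios of the table a true doubling still reads above 1. Attenuation is the general result; full masking needs the thresholds shown above.
- That Table 2 and Annex 3 contradict each other on CCO. On the criterion that names death they agree. The protocol does not classify all-cause death as gradual in onset; the tension arises because the category includes gradual deaths.
- That CCO should be crossed out and cohort or case-control used as the safe choice. In the same model the unadjusted case-control estimate is further from the truth. Adjustment may narrow the gap, but only where declining health is recorded, and section 9.8 itself expects unmeasured confounding.

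**Conclusion.** The point holds in a limited form. The CCO rating for all-cause death should be conditional, because the protocol recognises the mechanism for SCCS and omits it for CCO, and because the required case-time-control step addresses a different bias. Under the assumed inputs the null odds ratio is about 0.92 to 0.62, and a true doubling reads about 1.83 to 1.24. The range rests on a decline that covers the case window more than the control window; it shrinks to nothing when both are covered, and it does not arise for unforeseen deaths. Neither the frequency nor the timing of deferred vaccination before death can be taken from the protocol. For a mix of all deaths no investigator can take it as given that the two windows are equally affected, so an unqualified tick is not supported, and neither is a cross. This is a cheap improvement to the guidance.

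**What to change.** Change the CCO entry from a tick to O in the all-cause death row of Table 2 and in the Annex 3 row on events that censor observation of exposure. Table 2 uses only ticks and crosses, so the meaning of O must be carried over from the Annex 3 legend. Add a footnote in the style of footnote a, for example: *Suitable only if illness before the event does not change the likelihood of vaccination between the case and control windows; the case-time-control adaptation does not correct for such a change.*

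Keep the tick for sudden death. Do not mark CCO as unsuitable, and do not present cohort or case-control as free of this bias: for all-cause death they need adjustment for declining health.

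The cost is two cells, one legend entry and one footnote. The downside is that an investigator who wants CCO for all-cause death must first check the assumption. The Annex 3 row also names myocardial infarction, so the same check would be read as applying there.

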9.1 Study Design

Note to future investigators: Feasibility assessment is a necessary step before implementing the actual signal evaluation study (Yih, 2012; Willame, 2016). For each of the study design, inclusion and/or exclusion criteria for subjects should be defined upfront.

Please choose the template description of the appropriate design you choose and delete other design descriptions

9.1.1 Cohort

Retrospective (multi)-database cohort study where index <<COVID-19 vaccinated>> subjects and reference (subjects not vaccinated with << COVID-19 vaccine>>: reference cohort) are compared for occurrence of << event>>.

The comparison cohort will be matched using as example frequency matching or propensity score matching for important covariates such as age, sex and comorbidities (including COVID-19 infection prior to reference date) and markers of health care utilization (Austin, 2011). The comparison cohort could be the following:

- A concurrent comparison cohort including subjects not vaccinated with <<COVID-19 vaccine>> at the time of study start, identified at the same date (+/- 7 days – eg. anchored on a healthcare visit or pharmacy dispensing) of the exposure date (1st vaccine dose in case of multi-dose vaccine) of the matched vaccinated subjects. This calendar date time matching will allow to control for the variation in the SARS-CoV2 circulation and will minimize the risk of immortal time bias given that the time period before vaccination is immortal. To test for the presence and magnitude of immortal time, the time

difference between cohort entry and the date of start of vaccine distribution should be calculated for each cohort member and the frequency distribution of immortal time compared between the vaccinated and unvaccinated cohorts.

- If <<COVID-19 vaccine>> is distributed concurrently with the seasonal influenza vaccine, persons receiving both <<COVID-19 vaccine>> and the seasonal influenza vaccine could be compared with those receiving the influenza vaccine alone.
- A comparison cohort including subjects vaccinated with alternative <<COVID-19 vaccine>> in the same week as the matched index subjects. This time matching will allow to control for the variation in the SARS-CoV2 circulation.
- In the instance where the risk period of <<event>> is well known, the comparison cohort may be the same persons as the index cohort, with the comparison person time chosen after the ending of the risk window. Time trends in events cannot be controlled for in this manner.

[figure not shown]
The incidence rate ratio of the <<event>> is calculated comparing the incidence rate in index with that in the comparison cohort. The required follow-up time will depend on the event under evaluation, this follow-up time should take into account the vaccination schedule (**Figure 1**).

For example, for the evaluation of Guillain Barre Syndrome (GBS), a follow-up time period of at least 42 days should be applied after vaccine dose 1. In case a second/third vaccine dose is recommended or inadvertently administered, the follow-up period should be classified by dose and be extended for an additional 42 days after dose 2/3.

As a second example, for the evaluation of anaphylaxis, a risk period of 48 hours should be considered after each vaccine dose.

Risk periods are not yet known for COVID-19 vaccines and may depend on the platform as well as latency time of the <<event>> and the time it takes to have a diagnosis of <<event>> in a specific health care system. General recommendations are to have at least 2 months of follow-up for events with short latency, and 3 years for events with long latency.

Figure 1. Cohort design

9.1.2 Matched case-control

[figure not shown]
Retrospective (multi)-database case-control study where COVID-19 vaccination status is compared between cases (subjects who experienced << event>>) and controls (subjects who did not experience << event>>) in a specific time window.

Cases and controls should be matched on strong risk factors for the event and we recommend at least: age (year of birth), sex, and database (in case of multiple databases used) as well as calendar time. Controls should arise from a population where prior probability of exposure is the same as for the cases and be eligible to become and observed as a case if they develop the event of interest at a later date. As such persons may serve as control prior to becoming a case and may serve as a control for multiple cases (Richardson, 2004).

Index date for cases should be the disease date (preferably date of onset or first symptoms, otherwise diagnosis), the index date for the controls should be the index date of the corresponding cases. The calendar time matching, controls for confounding due to time related issues (e.g. circulation of SARS-Cov-2). Controls should be sampled using incidence density sampling (Lubin, 1984). For each subject in the database the start and end of follow-up is calculated, exclusion criteria are applied to all subjects and upon occurrence of an exclusion criterion, the follow-up time is censored. For each case, controls subjects who are actively registered in the data source at the index date of the case can be sampled or all eligible controls may be used (recommended if stratified analysis are conducted) (**Figure 2**).

In a case-control study, the aim is to compare the exposure during a specific time window between cases and controls. The time window prior to index date should be disease-specific plus the latency time period for the event under evaluation (e.g. for long latency events). For events with long latency, the risk window should be shortened or divided in small intervals to be able to assess the pattern of risk across different time windows. General recommendations are to have a time window of at least 2 months for events with short latency, and 3 years for events with long latency.

Figure 2. Case-control design

